## 1.3 Study Design

This single center open-label pilot study will enroll 10 adults with genetically-confirmed Becker muscular dystrophy, who will receive the purified nutritional extract (-)-epicatechin 100mg/day orally for 8 weeks. After screening visits, participants will be enrolled in the study if they meet all inclusion criteria. They will be evaluated at baseline and at screening, day 1, and weeks 1, 2, 4 and 8. The main criterion for success of the study will be presence of one or more biologic or strength and performance outcome measures (Aims 1 and 2 below) that yield a response magnitude that allows for sufficient power in a Phase II B study with a sample size of 30 individuals.

Evaluations of efficacy will include:

- Assessment of peripheral blood creatine phosphokinase, follistatin, (-)-epicatechin pharmacokinetics, blood lactate during exercise, and baseline and post-treatment mRNA and miRNA biomarker profiles.
- Assessment of baseline and post-treatment muscle biopsy by histology, Western blot, immunostain and electron microscopy.
- Assessment of strength by isokinetic dynamometry and quantitative grip testing, exercise performance during a standardized recumbent cycle test, muscle perfusion of the quadriceps by NIRS during the exercise test, a 6-minute walk test, and body composition by dual-energy x-ray absorptiometry (DEXA).

Evaluations of safety will include comprehensive review of

- vital signs, height and weight
- medical history
- physical and neurological exam
- previous and concomitant medication history
- electrocardiogram
- laboratory safety panels for hematology and coagulation, standard blood chemistries (lipid, hepatic and metabolic profiles)

This is a greater than minimal risk study with prospect for direct benefit. A medical monitor will review safety-related evaluations throughout the duration of the study.

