## 6 RESEARCH DESIGN AND METHODS

### 6.1 Selection and Withdrawal of Participants

#### 6.1.1 Criteria for Enrollment

Ten participants will be studied in this initial pilot project.

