**Table 3: Study procedures**

Event	Screening  (Week -2 to Day 1)	Baseline (Day 1)	Week 1	Week 2	Week 4	Week 8	Early with- drawal
Informed consent	X						
Medical history	X	X		X	X	X	X
Vital signs	X	X		X	X	X	X
Physical examination	X	X		X	X	X	X
Blood & urine collection (safety, efficacy, PK )	X	X		X	X	X	X
ECG	X	X		X	X	X	
Other medications and dietary supplements	X	X			X	X	X
Adverse events		X		X	X	X	X
Functional assessments strength, 6MWT, recumbent graded exercise test, NIRS, PFTs		X			X	X	X
Blood tests: baseline and efficacy		X			X	X	X
Muscle Biopsy Tests: baseline and efficacy		X				X	
Dispense Epicatechin		X		X			

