## 8 ASSESSMENT OF EFFICACY

### 8.1 Laboratory Efficacy Parameters

- Peripheral Blood Tests

Peripheral venous blood will be collected at points specified in the study visit chart to evaluate:

- Creatine phosphokinase (CPK)

- Follistatin
  - mRNA and miRNA biomarker profiles
  - Pharmacokinetics: epicatechin metabolites [serum tested at trough, 2 hours (Tmax), 4 hours after dose at baseline, week 2, week 4 and week 8].
  - Blood lactate testing during exercise: Blood lactate levels will be collected at baseline and 2-minute intervals by finger-stick or ear-stick during 6-minute cycle testing.
- Muscle Biopsy (Biceps Brachii)

Open biopsies of the mid-biceps will be conducted at baseline and after 8 weeks of study medication dosing. The muscle biopsy samples will be collected by open biopsy or according to standard hospital procedures. The minimum amount of muscle tissue required is a small piece of muscle of at least 0.5 x 1.0 x 1.0 cm. If possible, the tissue collected will be of sufficient size to provide 4 (four) pieces of tissue (each 0.5x0.5x0.5cm). Muscle for histological evaluation will be sent fresh to hospital pathology. Muscle tissue for evaluation at outside labs will be immediately frozen in liquid nitrogen-cooled 2-methylbutane and stored at -80°C or -70°C till shipment. Biopsy at baseline will be collected from the lateral aspect of the midpoint of the biceps muscle without the use of depolarizing agents or Bovie catheterization prior to tissue extraction. Biopsy at 8 weeks will be collected from medial aspect of the midpoint of the biceps muscle of the same arm, and must be separated by a margin of at least 1cm to avoid scar tissue from the earlier biopsy.

Histology samples will be evaluated ([name] lab, UC Davis) to examine:

- Fiber size variation
- Tissue necrosis
- Degree of central nucleation
- Presence of basophilic/regenerating fibers
- Fiber type (myosin IHC stains)
- NADH-TR and succinic dehydrogenase (mitochondria)

Muscle biopsy samples will be examined by Western blot ([name] lab, UC San Diego) to evaluate:

Initial Phase (done immediately upon biopsy)

- Muscle regeneration: follistatin, MyoD, myogenin, dystrophin, sarcoglycans, dysferlin
- Oxidation/oxidative stress: SOD1, SOD2, catalase, GSK, nNOS, eNOS
- Mitochondrial function: ETC-I, ETC-V, mitofilin, porin
- Transcriptional regulation: PGC1-alpha
- Collagen deposition: Collagen I, collagen III, fibronectin

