## **11 STATISTICS**

Presented herein is the overall analysis plan. The main criterion for success of the study will be presence of one or more biologic or strength and performance outcome measures (Aims 1 and 2) that yield a response magnitude that allows for sufficient power in a Phase II B study with a sample size of 30 individuals. Analysis, employing both statistical and graphical presentations of data, will generally proceed from descriptions and simple comparisons to multiple variable models. This will help to ensure proper understanding of the data at each level before proceeding to the next. Descriptive analysis of means and proportions will characterize study participants overall as well as evaluate assumptions of normality and homoscedasticity. Any significant departures from these assumptions especially for the measurement variables will lead to normalizing or variance stabilizing transformations or, in the unlikely event these are not successful, to conversion to ranks. Baseline and screening measures will be used to calculate test-retest reliability using the intraclass correlation coefficient. Level of statistical significance is set at  $<0.05$ . Simple comparative analyses involving chi squares ttests and correlations will be used to assess and understand simple relationships, including defining first order interactions. Where possible we will perform longitudinal analyses using mixed models (using xtreg or xtmixed in STATA 12) to evaluate raw scale and percent change over time in study outcomes measures. These procedures will allow us to account for fixed and random effects as well as correlation between observations when we introduce repeated measures on the same individuals. If feasible with the small number of participants in the study and because there is little available data for individuals with Becker muscular dystrophy, this pilot data will be used to determine estimates of minimally important clinical difference (MCID) for each measure (defined as  $1/3$  S.D. for the population). Safety data will be compiled as tables of frequency and severity of adverse events by body system.

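### Mixed models are named for 10 participants without a small-sample reference, estimator or random-effects structure; under z inference the 0.05 level would really be about 0.06 to 0.10

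*Combined protocol and SAP*

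**What the plan says.** Section 1.3 gives the size and design: "This single center open-label pilot study will enroll 10 adults with genetically-confirmed Becker muscular dystrophy". Section 6.1.1 repeats the number: "Ten participants will be studied in this initial pilot project".

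Section 11 fixes the level ("Level of statistical significance is set at" below 0.05) without saying whether tests are one- or two-sided. It describes a progression from descriptive work and simple comparisons to multivariable models. For the simple stage: "Simple comparative analyses involving chi squares ttests and correlations will be used". For change over time: "Where possible we will perform longitudinal analyses using mixed models (using xtreg or xtmixed in STATA 12", followed by "These procedures will allow us to account for fixed and random effects as well as correlation between observations". It names no estimator, random-effects structure, reference distribution or denominator degrees of freedom. Its only remark on the small number of participants concerns estimating the minimal important difference.

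The number of visits differs by outcome. For biopsies, Section 8.1 says: "Open biopsies of the mid-biceps will be conducted at baseline and after 8 weeks of study medication dosing". In Table 3 the row "Functional assessments strength, 6MWT, recumbent graded exercise test, NIRS, PFTs" is marked at Baseline, Week 4 and Week 8. The efficacy blood row has the same three visits, and the general blood collection row adds Week 2.

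**The concern.** With 10 people, a variance estimated on 9 to 29 degrees of freedom is itself uncertain. A normal reference ignores that uncertainty, and ML also biases the variance downwards. A mixed model reported this way gives intervals that are too narrow and rejects a true null more often than 5% of the time. The two-visit outcomes suffer most, and these are the muscle biopsy measures that Section 1.2 treats as primary.

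The plan also does not say which result governs if a paired t-test and a mixed model of the same change disagree. At two visits the same contrast could be significant against z and not against t, and either could be reported.

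**Working it through.** The 0.05 is a chosen setting, so there is no derived figure to reproduce. As a benchmark, a two-sided paired t-test on 9 df has size exactly 0.0500 under normality.

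**Inputs from the documents:** n = 10 (Sections 1.3 and 6.1.1); level 0.05 (Section 11); m = 2 visits for biopsy (Section 8.1), 3 for functional tests and 4 for general blood collection (Table 3).

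**Assumptions, not in the documents:** two-sided tests, normal reference (critical value 1.96), complete balanced data, no true change.

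**Step 1. Random intercept, people do not differ in slope.**
- df = (n-1)(m-1) with categorical time, or n(m-1)-1 with linear time.
- REML size = 2 × P(t_df > 1.96).
- ML size = 2 × P(t_df > 1.96 × √(df / (n(m-1)))).

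| Visits | df (categorical / linear) | REML, z | ML, z |
|---|---|---|---|
| 2 | 9 / 9 | 0.082 | 0.096 |
| 3 | 18 / 19 | 0.066 / 0.065 | 0.079 / 0.071 |
| 4 | 27 / 29 | 0.060 / 0.060 | 0.074 / 0.064 |

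With a t reference on the same df and the REML variance, every row returns to 0.050.

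**Step 2. Interval width at two visits.** The 97.5% point of t on 9 df is 2.262. Against REML with z, the correct interval is wider by 2.262/1.960 = 1.154, or 15%. Against ML with z it is wider by 1.154/√0.9 = 1.217, or 22%.

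**Step 3. Three visits, people differ in slope.** The documents give no slope variance, so the ratio of the SD of true 8-week change to the residual SD is varied. Simulated size (200,000 replicates) of the Week 8 minus Baseline contrast, categorical time, random intercept only:

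| Ratio | REML, z | ML, z | REML, t on 18 df | Paired t, 9 df |
|---|---|---|---|---|
| 0 | 0.065 | 0.079 | 0.050 | 0.050 |
| 1 | 0.092 | 0.108 | 0.072 | 0.050 |
| 2 | 0.131 | 0.151 | 0.107 | 0.050 |
| 3 | 0.156 | 0.177 | 0.131 | 0.050 |
| 20 | 0.198 | 0.219 | 0.170 | 0.050 |

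A linear time slope behaves similarly: 0.092 (REML) and 0.100 (ML) at ratio 1, 0.134 and 0.144 at ratio 2, 0.212 and 0.222 at ratio 20. With four visits and linear time it reaches 0.302 and 0.310 at ratio 20.

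**Step 4. Random slope fitted, z reference, three visits, linear time.** Over ratios from 0.5 to 5, size is 0.058-0.082 (REML) and 0.067-0.096 (ML). The excess over about 0.10 in Step 3 therefore comes mainly from leaving out the random slope. A t reference alone does not remove it (fourth column). The paired t-test holds 0.05 at every ratio.

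**The case against.** The strongest reply is that the plan never commits to z inference. It names two commands, says that both fixed and random effects will be accounted for, uses mixed models only where possible, and also names t-tests, which are exact at this sample size under normality. In a single-arm pilot meant to size a later trial, a shift from 0.05 to between 0.06 and 0.10 on exploratory p-values is small.

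Much of this stands. The z reference is an assumption, the effect is confined to outcomes analysed this way, and the point is minor. What does not stand is that naming t-tests settles it. Section 11 gives them the role of understanding simple relationships, assigns change over time to mixed models, and does not say which result is inferential.

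A reader might draw three stronger conclusions that the documents do not support.
- That the error rate has a ceiling of 15%. That figure depends on an assumed slope-SD ratio of about 2 and an omitted random slope. Larger ratios give more, fitting the slope gives less, and the plan does not choose a random-intercept model.
- That inflated p-values decide whether the study succeeds. The criterion in Sections 1.3 and 11 is a response large enough to power a later study of 30. It contains no p-value threshold, and z or t leaves the estimated change and its SD as they are. ML could shrink the SD by a factor of √0.9 = 0.949, about 5%, which is a small separate effect.
- That the intervals of every outcome are too narrow. A two-visit biopsy outcome tested by a paired t-test would not be affected.

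**Conclusion.** The concern holds as a minor one. The plan secures its 0.05 level only if the unstated choices happen to be the right ones. If inference is large-sample z, the true level is about 8-10% for two-visit biopsy outcomes and about 6-8% for outcomes with three or four visits when people share a common slope. At three visits it rises to about 9-15% if the slope SD is one to two times the residual SD and no random slope is fitted, with no ceiling at 15%. Per 20 null two-visit measures, expected false positives would go from 20 × 0.05 = 1.0 to 20 × 0.082 = 1.6 (REML) or 20 × 0.096 = 1.9 (ML).

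These figures assume two-sided tests, normal data and 10 completers. With 8 completers the two-visit sizes become 0.091 (REML) and 0.109 (ML).

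**What to change.** In Section 11, state that:
- for each continuous outcome, including the two-visit biopsy outcomes, the inferential result is the paired t-test of Week 8 minus Baseline on n-1 df (9 with 10 completers), with its confidence interval;
- mixed models are supportive, fitted by REML, with tests and intervals from a t distribution on small-sample df (Satterthwaite or Kenward-Roger);
- where there are three or more visits, the model includes a random slope or an unstructured covariance, because small-sample df alone do not protect a random-intercept model.

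The cost is a few lines of text and somewhat wider intervals (15-22% wider than z intervals at two visits). No new data or visits are needed.

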## 1.4 Specific Aims

**Aim 1. (Efficacy Primary Endpoint): Evaluation of (-)-epicatechin on blood and muscle tissue markers of mitochondrial biogenesis and muscle regeneration in adults with Becker muscular dystrophy.** Treatment with 8 weeks of (-)-epicatechin 100mg daily will induce mitochondrial biogenesis, muscle regeneration, and improved histological appearance in sarcomere morphology.

*Hypothesis:* (-)-Epicatechin will show evidence of mitochondrial biogenesis by Western blot assays of biceps brachii muscle biopsies through increases in ETC1, ETC5 and SOD2 proteins.

*Hypothesis:* (-)-Epicatechin will show evidence of induction of muscle regeneration through increases in PGC1a, decreases in acetylated (inactive) PGC1a, and increases in follistatin,

myogenin, and MyoD compared to pre-treatment baseline as determined by Western blot assays of biceps brachii muscle biopsies.

*Hypothesis:* Administration of (-)- epicatechin will be associated with increases in plasma concentrations of follistatin, a known hormonal regulator of muscle regeneration and a potential pharmacodynamic biomarker.

*Hypothesis:* Administration of (-)- epicatechin will be associated with electron microscopy evidence of increases in mitochondrial number and cristae density within the mitochondria compared to pre-treatment baseline.

*Hypothesis:* Administration of (-)- epicatechin will be associated with increased nNOS expression in skeletal muscle compared to pre-treatment baseline and this increased expression will be associated with improved muscle perfusion during exercise.

**Aim 2 (Efficacy Secondary Endpoints): Evaluation of the effects of (-)-epicatechin on exercise capacity in adults with Becker muscular dystrophy.** Individuals with Becker muscular dystrophy who receive 100mg/day of (-)-epicatechin will demonstrate improved exercise performance and strength that is associated with increases in mitochondrial biogenesis and muscle regeneration.

*Hypothesis:* Using the 6 minute walk test, and a standardized recumbent cycle exercise test with measurement of lactic acid levels, VO2 max, Work max, anaerobic threshold, and NIRS-defined skeletal muscle perfusion (measures of oxyhemoglobin, deoxyhemoglobin, and tissue saturation index) we will detect pre-/post-treatment differences in exercise capacity and endurance that will be clinically significant ( $\geq 5$ -10%) and reflect increases in mitochondrial biogenesis.

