*Hypothesis:* Changes in grip strength ( $\geq 5\%$ ), elbow flexion/extension isometric strength ( $\geq 5\%$ ), knee extension isometric muscle strength ( $\geq 1$  pound = 4.448 Newtons), pulmonary function derived maximal static airway pressures (MIP and MEP  $\geq 10$  cm H2O), and regional lean tissue mass by DEXA ( $\geq 2\%$ ) will be clinically significant and correlate with biomarker evidence for muscle regeneration and histological improvement in sarcomere morphology.

*Hypothesis:* Pilot data from exercise performance and strength evaluations in adults with Becker muscular dystrophy will determine the magnitude of response over time that will enable accurate power calculations for future clinical trials.

**Aim 3 (Safety Secondary Endpoints): Evaluation of safety and pharmacokinetic profiles of (-)-epicatechin in adults with Becker muscular dystrophy.** Assessments of safety will include a standard clinical safety panel including hematologic, hepatologic, renal and metabolic profiles. Pharmacokinetic studies will include repeat assessments of trough, 2 hour-post (peak) and 4-hour post dose (-)-epicatechin levels.

*Hypothesis (safety):* (-)-epicatechin given at 100mg/d orally will display an acceptable safety profile in BMD patients.

*Hypothesis (pharmacokinetics):* (-)-epicatechin given at 100mg/d orally in BMD patients will produce pharmacokinetic profiles similar to those seen in previously described studies in the literature.

**Aim 4 (Pilot Biomarker Endpoints): Pilot evaluation of disease- and epicatechin-specific circulating mRNA and miRNA blood profiles as pilot biomarkers for monitoring treatment efficacy.** Epicatechin stimulates follistatin expression in tissue and blood. In addition to its effects on muscle regeneration, follistatin is known to exert anti-inflammatory and anti-fibrotic effects via antagonism of activin and myostatin.

*Hypothesis:* Using gene array assays directed toward fibrosis- and inflammatory-oriented pathways, we expect treatment with (-)-epicatechin to induce detectable pre-/post-treatment differences in mRNA and miRNA expression that may be utilized as biomarkers of treatment effect for future clinical trials.

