### 6.1.3 Randomization

This is an open-label pilot study, and will not utilize randomization in the study design.

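### Section 11 models percent change without naming a primary scale or defining it; as a mean of individual ratios to one baseline it would lean upward by about the squared within-subject CV

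*Combined protocol and SAP*

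**What the plan says.** Section 11 (Statistics) states that, where possible, longitudinal mixed models will be used "to evaluate raw scale and percent change over time in study outcomes measures". It names no primary scale, does not define percent change and does not prespecify a log ratio. Transformation, or failing that ranks, is foreseen only if the data depart significantly from normality or equal variance.

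Aim 2 in Section 1.4 sets its thresholds on two kinds of scale:

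- Percentage: exercise capacity and endurance (at least 5-10%, for differences "that will be clinically significant"), grip strength (5%), elbow flexion/extension strength (5%), and "regional lean tissue mass by DEXA" (2%).
- Absolute: knee extension (1 pound) and maximal inspiratory and expiratory pressures, MIP and MEP (10 cm H2O).

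The Aim 1 blood and biopsy markers have no percentage threshold.

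On design, Section 6.1.1 says "Ten participants will be studied in this initial pilot project" and Section 6.1.3 says "This is an open-label pilot study, and will not utilize randomization in the study design". Sections 1.3 and 11 define success as at least one Aim 1 or Aim 2 measure with a response large enough to give adequate power in a Phase IIb trial of 30 people.

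**The concern.** A percent change divides by the baseline value. When that value is low by chance the ratio is inflated by more than it is deflated when the value is high by chance. With no true change, 100 falling to 80 is -20% and 80 rising to 100 is +25%; the average is +2.5%. So the mean of individual percent changes sits above zero when nothing has happened.

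A control arm would carry the same artefact and cancel it, but this study has none. Further visits do not help: if all changes share one baseline denominator, each post-baseline visit carries the same expected bias. Success needs only one measure among many, so a scale that leans upward, and leans most for the noisiest measures, could help the wrong measure go forward.

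**Working it through.** The plan states no SD, CV or power figure, so there is no number of its own to reproduce. The check asks how large the bias is and how it compares with the plan's thresholds and success criterion.

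**1. Bias under no effect.** Let c be the within-subject CV at each visit, with independent lognormal errors and no true change. With log-scale SD s, where s² = ln(1 + c²), the log ratio of two visits is N(0, 2s²). Then

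E[percent change] = exp(s²) - 1 = c².

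Simulation of 1,000,000 pairs agreed (2.24% at c = 15%, 8.98% at c = 30%). Normal errors give slightly more at c = 15% (2.4%).

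**2. A value for c.** The only noise figure is the 15% reproducibility requirement at screening (Section 6.1.2), whose metric is undefined. Three readings:

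| 15% read as | c | Bias c² |
|---|---|---|
| 95% limit of the test-retest difference | 0.15/(1.96·√2) = 5.4% | 0.3 points |
| SD of the difference | 0.15/√2 = 10.6% | 1.1 points |
| the CV itself | 15% | 2.25 points |

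Outside that range, by assumption: c = 1-2% (DEXA) gives 0.01-0.04 points against a 2% threshold; c = 30% (for example a biopsy marker) gives 9 points.

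For the bias alone to equal a threshold, c must be √0.02 = 14.1% (for 2%), √0.05 = 22.4% (for 5%) or √0.10 = 31.6% (for 10%).

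**3. Chance that the mean of ten null changes is at least 5%.** For the log-ratio summary this is 1 - Φ(ln 1.05 / (s·√(2/10))). At c = 15%, s = 0.149, so 0.0488/0.0667 = 0.73 and the probability is 23%. The arithmetic mean was simulated.

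| c | Mean percent change | Geometric mean ratio minus 1 |
|---|---|---|
| 5% | 1.8% | 1.4% |
| 10.6% | 21% | 15% |
| 15% | 34% | 23% |
| 30% | 58% | 36% |

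Most of the exceedance remains on the unbiased scale. It is sampling variation at n = 10.

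**4. Against the success criterion.** Power depends on effect divided by SD, and the percent scale inflates the SD too: SD = (1 + c²)·√((1 + c²)² - 1).

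- c = 10.6%: 0.0112/0.152 = 0.07 SD.
- c = 15%: 0.0225/0.218 = 0.10 SD.
- c = 30%: 0.09/0.473 = 0.19 SD.

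Assuming 80% power and two-sided 0.05, a paired comparison of 30 needs (1.96 + 0.84)/√30 = 0.51 SD; 15 per arm needs 2.80·√(2/15) = 1.02 SD. The chance that a null measure's observed standardised mean reaches 0.51 with ten participants is about 9% on the percent scale against 7% on the log scale at c = 10.6%, and 12-13% against 7% at c = 30%.

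**5. Test error.** The two-sided error rate of a t-test on percent change stays close to nominal (0.050 at c = 10.6%, 0.052 at c = 30%) but becomes lopsided: 0.034 upward and 0.018 downward at c = 30%.

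**The case against.** The other side has four good arguments.

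- Raw-scale change is planned alongside percent change and is free of this bias. Mean raw change divided by mean baseline also gives an essentially unbiased percentage. The plan never says that individual ratios to one baseline will be averaged. This stands, and it is why the point is conditional.
- Success is defined by power at 30 participants, not by crossing a 2-10% threshold, and the bias in SD units is well below what that power needs. This stands as to size. It does not remove the tilt, because one qualifying measure is enough and the Aim 1 markers count. Baseline and week-8 biopsies also come from different parts of the biceps (Section 8.1), which can add within-person variation.
- The transformation rule might catch the skew. It might, but it waits for a significant departure, which ten participants will often not show, and transforming a percent change already formed is not the same as analysing the log of the measurement.
- Chance at n = 10 matters more. It does, and the fix leaves it in place.

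A reader might go further and infer that response magnitudes are materially overstated across Aim 2 and that the next trial will be too small. The documents do not support that. They give no CV, the bias is slight at CVs of 5-10%, two Aim 2 criteria (knee extension and airway pressures) are absolute, and the criterion fixes the Phase IIb size at 30. Aim 2 also mentions power calculations for future trials, but no effect on those can be quantified from the documents.

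**Conclusion.** The point holds in a limited form. The plan leaves open both the primary scale and the construction of percent change, and the obvious construction is biased toward apparent benefit by about the squared within-subject CV. On the three readings of the 15% limit that is 0.3 to 2.3 percentage points against thresholds of 5% and 5-10%. It is negligible for lean mass if the CV is 1-2%, and large only for measures with a CV near 30%; both of those CVs are assumptions. The practical harm is a modest tilt in which measures look promising, and so in the power claimed for them at 30 participants.

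The figures assume independent lognormal errors of equal size at both visits, a single baseline, and, for the power comparison, 80% power and a paired or equal two-arm design. The plan states none of these. Severity is minor.

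**What to change.** In Section 11, replace the reference to percent change with wording to this effect: positive-valued outcomes will be analysed as log(value); percent change will be reported as the back-transformed mean log ratio (geometric mean ratio minus 1) with its confidence interval; and this figure will be compared with the percentage thresholds in Aim 2. Keep the raw-scale analysis, and state that it serves the absolute thresholds for knee extension, MIP and MEP.

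The change is a free improvement: no new data, visits or participants. Some reported percent gains become slightly smaller. Averaging two baselines would only about halve the bias (2.24 to 1.12 points at a CV of 15%), and Table 3 schedules functional assessments from baseline on, not at screening. Because chance variation remains, the confidence interval should be read with every point estimate set against a threshold.
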